APPENDIX C: PREGNANCY FOLLOW-UP

Pregnancy Follow-up Rationale

If a woman becomes pregnant during study participation, we will follow her for safety for the duration of the pregnancy and for 12 months following delivery for assessment of the neonate. In addition to the procedures described in section 8.4.2.3.4, we will perform additional research procedures to collect information regarding the delivery outcome and the health of the neonate/infant and mother over the months following delivery. This will allow an initial assessment of PK values after delivery as well as the effects of the investigational agent on pregnancy course and outcome, and infant health.

Pregnancy Follow-up Procedures

Participants who become pregnant during the study will be offered participation in the pregnancy follow-up phase and undergo an informed consent process (see section 10.1). Women who agree to participate will sign the pregnancy follow-up consent and will undergo the following assessments at the time of delivery:

- Hemoglobin measure using HemoCue
- Peripheral malaria test (RDT, blood smear, filter paper)
- Placental malaria using blood smear, filter paper
- Placental malaria histology
- PK blood draw
- AE assessment
- Breast milk to measure L9LS concentrations

After delivery, we will collect a breast milk sample at each of the scheduled infant visits described below.

At the infant follow-up visits during months 6, 9, and 12, 4 mL of blood will also be collected from the mother for detection of malaria and for PK analysis.

The neonate/infant and mother will undergo research assessments according to Table 6.

Table 6. Schedule of assessments for mother and neonate/infant participants.

Study Month	Month 0/ Delivery	3	6	9	12	Illness Visit	ET Visit
Window (days)	+7	±7	±7	±7	±7		
Clinical Procedures/Evaluations							
Heel/finger stick (infant)	X	X	X	X	X	X	X
Cord blood collection	X						
Weight (infant)	X	X	X	X	X	X	X
Ballard assessment (infant)	X						

Study Month	Month 0/ Delivery	3	6	9	12	Illness Visit	ET Visit
Window (days)	+7	±7	±7	±7	±7		
Apgar (infant)	X						
Length (infant)	X	X	X	X	X	X	X
Head circumference (infant)	X	X	X	X	X	X	X
Neurological assessment (infant)		X	X	X	X	X	X
Vaccination/EPI review ^a (infant)		X	X	X	X	X	X
AE assessment (mother and infant)	X	X	X	X	X	X	X
Breast milk sample (collected from mother)	X	X	X	X	X		X
Venous blood (collected from mother)			4 mL	4 mL	4 mL	4 mL	4 mL
Laboratory Evaluations							
Test	Tube	(infant blood volume)					
PK (heel/ finger stick)	SST	50 uL	50 uL	50 uL	50 uL	50 uL	50 uL
PK (cord blood)	SST	X					
Malaria blood smear/RDT ^b	N/A	(X)	(X)	(X)	(X)	3 to 4 drops	(X)
Hemoglobin	N/A		(X)	(X)	(X)	(X)	(X)

Abbreviations: AE, adverse event; ET, early termination; EPI, Expanded Programme of Immunization; PK, pharmacokinetics; RDT, rapid diagnostic test.

(X) indicates that no additional blood will be drawn; the test will be performed from blood collected for another evaluation listed.

^a Record vaccination information from EPI card.

^b Only performed if enough blood is available.

The month 12 visit will be the final study visit for participants; participation will be complete after this timepoint.

For both women and children, any AEs related to the blood collection procedures and all SAEs will be followed through resolution.

Compensation

Subjects will be compensated 3,000 CFA Franc for each study visit for the time and inconvenience of participation. Mothers and neonates/newborns will each receive compensation for study visits. Payment will be provided in cash after the completion of each visit. The parent/guardian will receive the payments for the neonate/infant participants.

Subjects will be provided with transportation to and from study visits but will not receive additional reimbursement for travel.

Additional Procedures and Processes

Refer to main protocol section [2.3.1](#), section [8](#), and section [10](#) for additional information related to risks, safety definitions and reporting, and human subject protection procedures.

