8.4.2.1.1 Severity Grading

The investigator will grade the severity of fever (by non-oral temperature reading) and each blood laboratory testing AE according to the “Mali Adverse Event Grading Scale” provided in [APPENDIX B: MALI ADVERSE EVENT GRADING SCALE](#). Events that are not gradable

using this table (e.g., urinalysis abnormalities) will be graded according to the “Guidance for Industry: Toxicity Grading Scale for Healthy Adult and Adolescent Volunteers Enrolled in Preventive Vaccine Clinical Trials” which can be found at: <https://www.fda.gov/media/73679/download>.

Events that are NOT gradable using either of the above specified tables will be graded as follows:

- Mild = grade 1
- Moderate = grade 2
- Severe = grade 3
- Potentially life threatening = grade 4
- Death = grade 5

NOTE: A subject death should always be reported as grade 5.

8.4.2.1.1.1 Laboratory Value Assessment and Clinical Significance Criteria

Except as specified below, ALL abnormal lab values of grade 1 or above are REPORTABLE.

Grade 1 and 2 abnormal laboratory values are considered CLINICALLY SIGNIFICANT, and are to be recorded in the research database, and reported, if they meet ONE or more of the following criteria:

- result in a study agent dosage adjustment, interruption, or discontinuation
- are accompanied by clinically abnormal signs or symptoms that are likely related to the laboratory abnormality (e.g., clinical jaundice)
- indicate a possible organ toxicity (e.g., elevated serum creatinine)
- result in additional/repeat testing or medical intervention (procedures/treatments) (e.g., ECG to evaluate arrhythmia potential with a high serum potassium; one or more ECGs to assess an elevated troponin level; potassium supplementation for hypokalemia)
- indicates possible over-dosage
- are considered clinically significant by the investigator or SMM

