APPENDIX B: MALI ADVERSE EVENT GRADING SCALE

Evaluation	Mild (Grade 1)	Moderate (Grade 2)	Severe (Grade 3)	Potentially Life-threatening (Grade 4)
Hematology and Biochemistry Values^{1, 2}				
Hemoglobin (Female) – gm/dL	8.0 – 9.0	7.0 – 7.9	6.0 – 6.9	< 6 and/or requiring transfusion
Hemoglobin (Male) – gm/dL	9.5 – 10.3	8.0 – 9.4	6.5 – 7.9	< 6.5 and/or requiring transfusion
WBC Increase – 10³/µL	11.5 – 15.0	15.1 – 20.0	20.1 – 25.0	> 25.0
WBC Decrease – 10³/µL	2.5 – 3.3	1.5 – 2.4	1.0 – 1.4	< 1.0 with fever
Neutrophil/Granulocyte Decrease³ – 10³/µL	0.80 – 1.00	0.50 – 0.79	< 0.50	< 0.50 with fever
Platelet Decrease – 10³/µL	100 – 110	70 – 99	25 – 69	< 25
Creatinine (Male) – µmol/L	124.00 – 150.99	151.00 – 176.99	177.00 – 221.00	> 221.00 and requires dialysis
Creatinine (Female) – µmol/L	107.00 – 132.99	133.00 – 159.99	160.00 – 215.99	> 216.00 and requires dialysis
Liver Function Tests/ALT – U/L	75.0 – 150.9	151.0 – 300.9	301.0 – 600.0	> 600.0
Other Values				
Fever⁴ – °C	37.5 – 37.9	38.0 – 38.4	38.5 – 39.5	> 39.5

Abbreviations: ALT, alanine transaminase; WBC, white blood cell.

¹ The laboratory values provided in the tables serve as guidelines and are dependent upon institutional normal parameters. Institutional normal reference ranges should be provided to demonstrate that they are appropriate.

² The clinical signs or symptoms associated with laboratory abnormalities might result in characterization of the laboratory abnormalities as potentially life-threatening (grade 4). For example, a low sodium value that falls within a grade 3 parameter should be recorded as a grade 4 hyponatremia event if the subject had a new seizure associated with the low sodium value.

³ Note: Neutropenias are graded and followed, but based on previous experience in African populations, should be interpreted with caution since lower values are more frequently observed in people of African descent. [28, 29]

⁴ Values presented are for non-oral temperature reading (i.e., axillary or no-touch), which is the preferred method at the study site. If oral temperature is taken, the US Food and Drug Administration toxicity grading scale will be used to grade fever.

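### Appendix C measures hemoglobin in infants, but the default grading rule is a sex-split table with no infant range, so one infant value can get different grades in a boy and a girl

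*Combined protocol and SAP*

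**What the plan says.** Table 6 of Appendix C covers mother and neonate/infant. It includes a row for "AE assessment (mother and infant)" from delivery to month 12 and at illness and early-termination visits. The laboratory block is headed "infant blood volume" and includes hemoglobin. Appendix C gives an initial look at infant health as one of its purposes.

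Appendix C contains no severity scale. It sends the reader to sections 2.3.1, 8 and 10 "for additional information related to risks, safety definitions and reporting, and human subject protection procedures".

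Section 8.4.2.1.1 grades in three tiers:

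1. "The investigator will grade the severity of fever (by non-oral temperature reading) and each blood laboratory testing AE according to the" Mali scale in Appendix B. No age limit or infant exception is given.
2. Events Appendix B cannot grade go to the "Toxicity Grading Scale for Healthy Adult and Adolescent Volunteers Enrolled in Preventive Vaccine Clinical Trials".
3. "Events that are NOT gradable using either of the above specified tables will be graded as follows": a generic scale from mild to death.

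In Appendix B, hemoglobin has two rows, "Hemoglobin (Female) – gm/dL" and "Hemoglobin (Male) – gm/dL". Footnote 1 treats the table's values as guidance tied to institutional normals and asks that those ranges be supplied. None is supplied for infants.

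**The concern.** Infants enter this adult trial only through Appendix C, and the grading rule was not adapted for them. Because Appendix B has a hemoglobin row for each sex, an infant value is gradable there and stops at the first tier. The rule then assigns a grade by sex, and nothing in the documents justifies a sex split in the first year of life.

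The grade has consequences. Reading the two statements on laboratory values in section 8.4.2.1.1 together, grade 3 and above is reportable without condition. Grades 1 and 2 are recorded and reported if at least one listed criterion is met. A value below grade 1 does not enter that scheme. Two infants with the same hemoglobin can therefore be handled differently because one is a boy. The trial is meant to prepare for studies in pregnant women, so each infant record will be read closely.

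**Working it through.** The plan states no figure on this point, so there is none to reproduce. The check applies the Appendix B cut-offs to each hemoglobin value h in steps of 0.1 g/dL.

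**Inputs (Appendix B, g/dL)**

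- Female: grade 1, 8.0–9.0; grade 2, 7.0–7.9; grade 3, 6.0–6.9; grade 4, below 6.
- Male: grade 1, 9.5–10.3; grade 2, 8.0–9.4; grade 3, 6.5–7.9; grade 4, below 6.5.

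The transfusion criterion for grade 4 is left out. Values above the grade 1 band count as ungraded.

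**Comparison of the two grades at the same h**

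| h (g/dL) | Girl | Boy | Values | Same? |
|---|---|---|---|---|
| below 6.0 | 4 | 4 | – | yes |
| 6.0–6.4 | 3 | 4 | 5 | no |
| 6.5–6.9 | 3 | 3 | 5 | yes |
| 7.0–7.9 | 2 | 3 | 10 | no |
| 8.0–9.0 | 1 | 2 | 11 | no |
| 9.1–9.4 | ungraded | 2 | 4 | no |
| 9.5–10.3 | ungraded | 1 | 9 | no |
| 10.4 and above | ungraded | ungraded | – | yes |

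- Values from 6.0 to 10.3: 5 + 5 + 10 + 11 + 4 + 9 = 44.
- Values with different grades: 5 + 10 + 11 + 4 + 9 = 39. Only 6.5–6.9 agrees within this window.
- The boy's grade is the higher one at all 39 values. The gap is two grades at 4 of them (9.1–9.4).
- The severe threshold (grade 3 or above) is crossed by one sex only at 10 values (7.0–7.9).
- A girl has no grade at 4 + 9 = 13 values (9.1–10.3) where a boy has grade 1 or 2.

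**How many infants**

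The plan has 192 women followed for 168 days: 192 × 168/365 = 88.4 woman-years. The documents give no pregnancy rate. At an assumed 0.5 to 4 per 100 woman-years, the expected number of pregnancies is 88.4 × 0.005 = 0.4 to 88.4 × 0.04 = 3.5 over both arms. With 3:1 allocation, a quarter of these (0.1 to 0.9) would be on placebo.

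**The case against.** The strongest reply is that this is a wording gap with almost no reach. Appendix C applies only after an unplanned pregnancy, despite required contraception, and with separate consent. The primary safety endpoint covers 7 days after dosing. Serious events are defined by seriousness, not grade. Pregnancy is excluded before the single dose and all enrollment is expected within 6 months, so infant grades are unlikely to bear on a pause or halt. Footnote 1 also leaves the cut-offs open to institutional ranges. All of this stands as a limit on size. It does not remove the defect: the default rule is explicit, and footnote 1 asks for ranges that are not provided for infants.

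A reader might infer several stronger things that the documents do not support:

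- *That infant events have no usable scale.* The generic third tier covers events that neither table can grade. It does not help hemoglobin, which Appendix B can grade.
- *That infant safety as a whole is mis-graded.* The documents give no infant reference range, so they cannot show which grade would be wrong. Appendix B is not labelled adult either; that is inferred from the trial population and the sex split.
- *That low newborn values escape grading.* This needs outside ranges. No infant hemoglobin at delivery is legible in Table 6, whose layout is damaged in the available text.
- *That a comparison of infant anemia by arm would be distorted.* None is planned. Section 9.4.5 analyzes randomized subjects who received product.
- *That 39 of 44 (89%) is a share of infants.* It is a share of grid points in a window that starts and ends where the two rows start and stop differing.

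**Conclusion.** Wrong as written, minor in reach. Section 8.4.2.1.1, reached through Appendix C, grades infant hemoglobin on a sex-split table with no infant range. Between 6.0 and 10.3 g/dL the sexes receive different grades at 39 of 44 values, including the severe threshold across 7.0–7.9. The effect is confined to the descriptive infant safety record.

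The conclusion rests on reading section 8.4.2.1.1 literally for infants, since no other rule is given, and on taking the Table 6 hemoglobin row as an infant test, which its block heading supports. The exact visits for that test cannot be confirmed. The count of 39 needs no outside figure. The number of pregnancies does, and is shown only for scale.

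**What to change.** - In section 8.4.2.1.1 and Appendix C, state that the Appendix B hemoglobin bands and the adult/adolescent scale apply to adult participants only.
- Attach to Appendix C an age-appropriate infant grading table without the adult sex split. The sponsor should choose the cut-offs and give their source.
- List infant events separately from adult events, with the raw hemoglobin value, age and sex beside each grade. With so few infants, the raw values will be more informative than the grades.

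The cost is one added table, one coding rule in the infant case report form, and two grading scales in the safety listings, which must be labelled so that adult and infant grades are not pooled.
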